Given the fact that participants will be randomized into the two arms, the outcome variables will likely be comparable between the two arms at baseline. As a result, the interaction effect between the treatment arm and follow-up time (while adjusting for covariates) will be tested in the longitudinal analysis to evaluate the difference between the two intervention arms because a significant interaction indicates the caregiver's outcome has followed significantly different trajectories in the follow-up period depending on the treatment arm. Missing values may be possible because 1) some caregivers may be lost to follow-up, and 2) some caregiving recipients can be deceased prior to the follow-up. Missing patterns will be inspected and multiple imputation methods, including regression imputation, propensity score imputation, and MCMC imputation will be considered based on the missing mechanism^47. All tests will be two-sided and a p-value less than or equal to 0.05 will be reported as statistically significant. Statistical Analysis Software (SAS software, version 9.4; SAS Inc., Cary, NC) will be used to conduct the proposed analysis.

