### Sample size considerations

The primary endpoint in this power analysis is the Zarit's caregiving burden score. Assuming 20% attrition rate at the 6-month follow-up, we plan to initially enroll totally 240 family caregivers who will be equally randomized into two will be equally randomized into two arms (120 per arm), and we expect a minimum of 100 caregivers per arm to complete the 6-month assessment. The sample size of 100 in each arm can guarantee 80% power at significance level 0.05 to detect the effect size of 0.28 standard deviation (SD)

difference between baseline and 6 months follow-up in a two-sided paired t-test. (See Table 4). Nicholas et al. reported the effect size of 0.33SD of Zarit's score from the REACH VA intervention (also between baseline and 6-month follow-up). While GP4C will use a different delivery strategy than used in the REACH II and REACH VA trials, core therapeutic materials and techniques of the intervention are maintained. Thus, we expect GP4C to have a similar impact on caregiver outcomes as observed in prior REACH II trial. Thus, we conclude that enrolling 120 caregivers per arm (100 available at 6 months) will achieve sufficient statistical power to detect the effectiveness of the proposed interventions, even if the GP4C full functionality intervention is slightly less robust than the original REACH interventions.

*Table 4. Sample size and power by effect size*

Effect size of 0.28 standard deviation (SD) difference		Effect size of 0.33 standard deviation (SD) difference	
Sample Size	Power	Sample Size	Power
70	.646	70	.777
80	.706	80	.830
90	.757	90	.872
100	.800	100	.905
110	.834	110	.929
120	.868	120	.948
130	.893	130	.962
140	.914	140	.972
150	.931	150	.980

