**Two specific staged AIMS are proposed in this study.**

**AIM 1. Advance the current proof-of-concept GP4C into a viable delivery system for the REACH II intervention.** Further development will include uploading the full breadth of REACH II education and skill-building materials, usability testing and updates to the user interface/user experience (UI/UX), creating a portal of delivery tools used by Dementia Care Specialist (DCS; i.e., interventionist), and establishing a comparable education-focused online system (Resources4Care; R4C) to be used in comparison to the multicomponent, skills-training GP4C system. Development activities will be conducted by the Baylor Scott & White Health (BSWH) Office of Digital Health with engagement of community-based organizations, family caregivers, and external advisors, with oversight by the GP4C research team.

**H1:** *Within 12 months of usability testing with 32 family caregivers, the GP4C research team will reach consensus with the BSWH Office of Digit Health and an external Advisory Committee that GP4C is a viable platform for online delivery of REACH II with R4C as an appropriate comparison condition.*

**AIM 2. Compare the relative impact of GP4C and R4C, both of which include access to a Dementia Care Specialist, on a wide range of family caregiver outcomes.** Family caregivers will be randomized to one of the two conditions and will complete an assessment battery at baseline and at the 6-month follow-up. Primary outcome measures will include burden, depression, social support, and caregiver's health and interaction with health care providers. Secondary outcomes will include caregiver stress, positive aspects of caregiving (PAC), cognitive change in care-recipient. The CBOs will designate a "GP4C Champion" to promote the enrollment of 240 family caregivers who have computer access and report regular use of the internet. Use of GP4C & R4C and contact with DCS will be recorded by the system as implementation data.

**H1:** *Family caregivers randomized to the GP4C condition will report greater improvement on primary and secondary outcomes as compared to family caregivers in the R4C condition.*

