### 4.3 Sample Size Considerations

The primary endpoint in this power analysis is the Zarit's caregiving burden score. Assuming 20% attrition rate at the 6-month follow-up, we plan to initially enroll totally 240 family caregivers who will be equally randomized into two will be equally randomized into two arms (120 per arm), and we expect a minimum of 100 caregivers per arm to complete the 6-month assessment. The sample size of 100 in each arm can guarantee 80% power at significance level 0.05 to detect the effect size of 0.28 standard deviation (SD) difference between baseline and 6 months follow-up in a two-sided paired t-test. (See Table 4). Nicholas et al. reported the effect size of 0.33SD of Zarit's score from the REACH VA intervention (also between baseline and 6-month follow-up). While GP4C will use a different delivery strategy than used in the REACH II and REACH VA trials, core therapeutic materials and techniques of the intervention are maintained. Thus, we expect GP4C to have a similar impact on caregiver outcomes as observed in prior REACH II trial. Thus, we conclude that enrolling 120 caregivers per arm (100 available at 6 months) will achieve sufficient statistical power to detect the effectiveness of the proposed interventions, even if the GP4C full functionality intervention is slightly less robust than the original REACH interventions.

*Table 4. Sample size and power by effect size*

| Effect size of 0.28 standard deviation (SD) difference |       | Effect size of 0.33 standard deviation (SD) difference |       |
|--|-------|--|-------|
| Sample Size  | Power | Sample Size  | Power |
| 70   | .646  | 70   | .777  |
| 80   | .706  | 80   | .830  |
| 90   | .757  | 90   | .872  |
| 100  | .800  | 100  | .905  |
| 110  | .834  | 110  | .929  |
| 120  | .868  | 120  | .948  |
| 130  | .893  | 130  | .962  |
| 140  | .914  | 140  | .972  |
| 150  | .931  | 150  | .980  |

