## 5 Outcome Measures

### Change from Baseline Caregiving Burden at 6 months

A 12-item version of the Zarit Caregiver Burden Interview. The Zarit Caregiver Burden Interview (ZBI) is an assessment tool for evaluating caregiver burden. The ZBI consists of 12 items representing a statement related to some aspect of perceived burden. Respondents (i.e., caregivers) rate each item ranging 0 (=never) to 4 (=nearly always). Total ZBI score is the summation of 12 items ranging from 0 to 48. Higher scores indicate greater burden.

[Time Frame: Baseline and six months]

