## 6 Statistical Methods and Analyses

Caregiver participants will be randomized to the two intervention arms (GP4C and R4C) with the ratio of 1:1. Primary and secondary outcomes, including the Zarit's caregiving burden interview, will be assessed at baseline and 6-month follow-up. Covariates in the analysis include demographic characteristics of the caregivers. Common descriptive statistics (mean, standard deviation, median, interquartile range for continuous variable; frequency and percentage for categorical variables) will be calculated for all covariates in each intervention arm and the two arms will be compared at baseline. Goals of our statistical analysis will be to evaluate the effectiveness of each intervention arm and to compare the two arms. For each intervention arm, the difference between 6-month follow-up and baseline will be computed. Paired t-test and Wilcoxon signed-rank test will be used to detect significant changes in outcome variables at 6-month follow-up since the baseline. Medians, means, and 95% confidence intervals of the differences will be calculated using both empirical percentiles and normal approximation. Multiple comparison adjustments, e.g., Holm-Bonferroni method and Hochberg procedure, will be implemented to control the family wise error rate when testing multiple outcome measures in Section 5.

The two intervention arms will be compared at each follow-up time and for the whole trial period. We will compare the two arms at 6-month follow-up using the two-sample t-test and Wilcoxon rank sum test for each of the two outcomes. The Anderson-Darling test will be used to check the normality assumption at baseline and follow-up times for the two outcome variables. If normal assumption is significantly violated then only nonparametric estimates and tests (i.e., median, IQR, empirical confidence intervals, Wilcoxon signed-rank test, and Wilcoxon rank sum test) will be reported, and data transformation, such as log and square root transformations, will be considered to normalize the outcome variables for further model-based testing. A pre-post analysis will be conducted to model the outcomes at 6-month follow-up to test the intervention arm and covariates adjusting the baseline measurements. The two arms will also be compared incorporating observations from baseline and follow-up in longitudinal analysis of covariance (ANCOVA) models or linear mixed-effects models having the follow-up time and adjusting for covariates.

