Given the fact that participants will be randomized into the two arms, the outcome variables will likely be comparable between the two arms at baseline. As a result, the interaction effect between the treatment arm and follow-up time (while adjusting for covariates) will be tested in the longitudinal analysis to evaluate the difference between the two intervention arms because a significant interaction indicates the caregiver's outcome has followed significantly different trajectories in the follow-up period depending on the treatment arm. Missing values may be possible because 1) some caregivers may be lost to follow-up, and 2) some caregiving recipients can be deceased prior to the follow-up. Missing patterns will be inspected and multiple imputation methods, including regression imputation, propensity score imputation, and MCMC imputation will be considered based on the missing mechanism^19. All tests will be two-sided and a p-value less than or equal to 0.05 will be reported as statistically significant. Statistical Analysis Software will be used to conduct the proposed analysis.

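### SAP 4.3 states 80% power for burden at an unadjusted 0.05, while SAP 6 places burden under family-wise error control over a family whose size is not fixed

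*SAP*

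**What the plan says.** SAP 4.3 sizes the trial on burden alone. It says 100 per arm "can guarantee 80% power at significance level 0.05 to detect the effect size of 0.28 standard deviation (SD) difference" in a two-sided paired t-test from baseline to 6 months. It concludes that the sample suffices "even if the GP4C full functionality intervention is slightly less robust than the original REACH interventions". The protocol's section on sample size has the same text ("The sample size of 100 in each arm can guarantee 80% power at significance level 0.05") and the same Table 4.

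The protocol's Data Analysis section has no multiplicity adjustment and closes with "All tests will be two-sided and a p-value less than or equal to 0.05 will be reported as statistically significant". SAP 6 adds one. With Holm-Bonferroni and Hochberg as examples, adjustments "will be implemented to control the family wise error rate when testing multiple outcome measures in Section 5". Section 5 opens with "Change from Baseline Caregiving Burden at 6 months".

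The documents give three cues to the size of the family:
- SAP 5 has ten entries, none labelled primary. They include the usability questionnaire and the distress composite.
- SAP 2, Aim 2, names five primaries: "Primary outcome measures will include burden, depression, social support, and caregiver's health and interaction with health care providers".
- SAP 6, in its between-arm paragraph, refers twice to a pair of outcomes without naming them.

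SAP 6 keeps the sentence "a p-value less than or equal to 0.05 will be reported as statistically significant" and does not say whether that p-value is raw or adjusted. The protocol's Measures and Outcomes section calls burden the signature outcome because the power calculation uses it. It gives no testing order.

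**The concern.** The error rule changed between protocol and SAP, but the power statement did not. Under Holm or Hochberg with m outcomes, burden's threshold lies between 0.05/m and 0.05, depending on the other p-values. Power computed at 0.05 is then a ceiling, not a guarantee.

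Two things are at stake. First, the reassurance that a somewhat weaker intervention would still be detected rests on the unadjusted level. Second, the decision rule is open. With five outcomes, a burden p-value between 0.01 and 0.05 is significant if the 0.05 sentence is read as applying to raw p-values. Under the family-wise rule it may not be, depending on the other outcomes. That should be settled before results are seen.

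**Working it through.** **Inputs from the documents.** Two-sided paired t-test; n = 100 completers per arm; d = 0.28 SD, with 0.33 SD as the effect cited from REACH VA; alpha 0.05; stated power 0.800 and 0.905 (SAP 4.3 and Table 4).

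**Assumptions, not in the documents.** The family size m, the effects on the other outcomes, and the correlation between outcomes (0 to 0.5). Each outcome counts as one test.

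**Formula.** Power = P(|T| > t(1 − a/2; n − 1)), where T is noncentral t with n − 1 degrees of freedom and noncentrality d√n. At d = 0.28 and n = 100 the noncentrality is 0.28 × 10 = 2.8.

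**Step 1: reproduce the plan.** At a = 0.05 the critical value is 1.984. Power is 0.792 against 0.800 stated (normal approximation 0.7996). At 0.33 SD it is 0.905, as stated. The 0.28 column of Table 4 fits an effect of about 0.283 before rounding.

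**Step 2: first-step level 0.05/m, d = 0.28.**
- m = 2, a = 0.025: 0.70.
- m = 5, a = 0.01 (critical value 2.626): 0.570.
- m = 10, a = 0.005: 0.475. Ten is the count of Section 5 entries. It is also five outcomes tested in each of two arms.

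**Step 3: credit the stepwise procedures.** Holm and Hochberg were applied to simulated paired differences (n = 100, 40,000 draws, exact t). Ranges span the two procedures and the correlations.

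| Burden effect | Family | Other outcomes | Power for burden |
|---|---|---|---|
| 0.28 SD | none | – | 0.79 |
| 0.28 SD | 2 | null | 0.70 |
| 0.28 SD | 2 | moves by 0.28 | 0.75–0.77 |
| 0.28 SD | 5 | all null | 0.57 |
| 0.28 SD | 5 | two of four move by 0.28 | about 0.61 |
| 0.28 SD | 5 | all move by 0.28 | 0.67–0.72 |
| 0.28 SD | 5 | all move by 0.33 | 0.72–0.76 |
| 0.28 SD | 5 | all move by 0.40 | 0.77–0.79 |
| 0.33 SD | none | – | 0.905 |
| 0.33 SD | 5 | all null | 0.75 |
| 0.33 SD | 5 | one of four moves by 0.33 | about 0.77 |
| 0.33 SD | 5 | two of four move by 0.33 | about 0.79–0.80 |
| 0.33 SD | 5 | all move by 0.33 | 0.84–0.88 |

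The 0.72 at the top of the row where all move by 0.28 uses the unrounded 0.283 SD. At exactly 0.28 the top is 0.71.

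**Step 4: the same loss in other units, at the five-outcome first step (0.01).** The effect detectable with 80% power rises from 0.283 to 0.348 SD. Completers needed per arm at 0.28 SD rise from 103 to 153. At 20% attrition that is 103/0.8 = 128.75, so 129 enrolled per arm, against 153/0.8 = 191.25, so 192.

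**The case against.** SAP 4.3 says openly that its figure is at 0.05 and does not claim adjusted power. Sizing on one signature outcome is defensible, and the SAP describes the study as Phase 1. That stands as far as it goes: the sizing choice is acceptable once a testing order is written. None is written now, and SAP 6 covers burden without exception.

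A reader might infer that the trial simply has some fixed lower power, such as 0.57 or a band in the 0.6s and low 0.7s. The documents do not support that. They do not fix a family of five, and they give no effect sizes for the other outcomes. With two outcomes the loss is smaller; if the other outcomes have larger effects than burden, power returns almost to 0.79. Nor does the margin for a weaker effect disappear under every reading: with two outcomes, power at 0.33 SD is still 0.845 at the first step.

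It is also fair to say that these figures concern a within-arm paired test, while the Aim 2 hypothesis is between arms. The paired test is the one SAP 4.3 powers, and the adjustment sentence ends the paragraph that specifies it, so the comparison is like for like. A two-sample t-test at 0.28 SD with 100 per arm has 0.50 power before any adjustment. That is a separate issue.

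**Conclusion.** The inconsistency is certain: the power stated for burden ignores the error control that the SAP commits to, and the adjusted level cannot be determined from the text. At 0.28 SD with 100 completers, no adjustment scenario exceeds the unadjusted 0.79.

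The size is conditional. Across the readings the text allows, power runs from 0.475 (first step, ten tests) to about 0.79 (others with clearly larger effects). If the family is the five Aim 2 primaries, the room for a weaker effect is lost or nearly lost unless most of the other outcomes also respond. Even at the full 0.33 SD, power is 0.75 if the others are null, about 0.77 if one moves and about 0.79 to 0.80 if two move. It is comfortably above 80% (0.84 to 0.88) when all move. Confidence is high for the contradiction and lower for any single figure, since family size, other effects and correlations are assumed.

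**What to change.** In SAP 6, name the family, one procedure, and the one test per outcome whose p-value enters it. Correct the references to a pair of outcomes to match. Then choose one rule:

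- **(a) Burden first.** Test burden at two-sided 0.05. Only if it is significant, apply Holm to the remaining Section 5 outcomes, or to the other primaries and then to the secondaries. Either form keeps the secondaries under the control SAP 6 now gives them; limiting the family to the five primaries would drop them.
- **(b) Burden inside the family.** In SAP 4.3 and the protocol's sample size section, replace the 80% with burden's power at the adjusted level under stated scenarios, with the first-step level as the lower figure.

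Under either rule, compute SAP 4.3 for the test that enters the family. If that is the between-arm term, paired-test figures do not apply. State in SAP 6 that 0.05 applies to adjusted p-values for outcomes in the family; under (a), burden is judged at 0.05 directly.

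The cost is wording, with no new data. Under (a) the other outcomes are tested only if burden is significant. Under (b) the plan states a lower power. A family containing provider interaction also needs one score for its nine items, for which SAP 5 gives no total. The change does not cure low between-arm power.

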#### Program Evaluation of GP4C/R4C

Assessment of attitude toward GP4C/R4C system:

A 30-items of USE questionnaire will evaluate participant's attitude toward the GP4C system. The USE questionnaire includes four areas: assess usefulness (8 items), ease of use (11 items), ease of learning (4 items), and satisfaction (7 items). Respondents rate agreement with the statements, ranging from strongly disagree (=1) to strongly agree (=7). Total scores are the summation of items on each area. Higher scores in each indicate a more useful, easier to use, easier to learn, and more satisfied on their experience.

[Time Frame: At six months only]

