#### A Composite Psychological Distress Score

A composite score of psychological distress will be constructed. Three measures, depression (CES-D), caregiver stress (PSS), and NPI-Q Distress, will be transformed linearly to have a range from 0 to 100 and then combined with the same weight. This replicates the creation of a dementia burden composite score used in the literature.

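### The SAP's multiplicity rule points to one unlisted family across Section 5, so the primary/secondary split plays no part in testing, and it is unclear which tests the rule governs

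*SAP*

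**What the plan says.** SAP Section 2 (Aim 2) ranks the outcomes. "Primary outcome measures will include burden, depression, social support, and caregiver's health and interaction with health care providers", which makes five. "Secondary outcomes will include caregiver stress, positive aspects of caregiving (PAC), cognitive change in care-recipient", which makes three. The Aim 2 hypothesis then covers both tiers together: GP4C caregivers "will report greater improvement on primary and secondary outcomes as compared to family caregivers in the R4C condition".

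SAP Section 6 has one multiplicity rule, under which adjustments "will be implemented to control the family wise error rate when testing multiple outcome measures in Section 5". No single procedure is fixed, since two methods are given only as examples: "Multiple comparison adjustments, e.g., Holm-Bonferroni method and Hochberg procedure". Section 6 uses the primary/secondary split only to say when outcomes are measured: "Primary and secondary outcomes, including the Zarit's caregiving burden interview, will be assessed at baseline and 6-month follow-up". It sets out no separate primary family, testing order, gatekeeping or alpha allocation. The Data Analysis section of the protocol has no multiplicity rule.

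SAP Section 5 has ten unlabelled headings: burden, depression, self-rated health, social support, interaction with health care providers, stress, positive aspects of caregiving (PAC), NPI-Q, the USE usability questionnaire and a composite distress score.

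- USE is collected at six months only, in four areas: "Total scores are the summation of items on each area".
- The composite reuses listed measures: "Three measures, depression (CES-D), caregiver stress (PSS), and NPI-Q Distress, will be transformed linearly to have a range from 0 to 100". It is not among the outcome measures in the protocol.

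**The concern.** A confirmatory family should hold the claims that the trial wants to establish. Here the plain reading places a usability rating, and a composite that adds no new measurement, on the same footing as the five primary outcomes. Each extra member tightens the threshold that a primary must meet. The ranking in Aim 2, which should say which results carry the trial, does nothing in the analysis.

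A second difficulty is scope. The adjustment sentence ends the paragraph on paired tests within each arm. The next paragraph, on comparisons between arms, mentions two outcomes without naming them and gives no adjustment. The last paragraph of Section 6 then applies 0.05 to every test. Two analysts could follow this text and reach different conclusions about the Aim 2 hypothesis from the same data: one might adjust ten between-arm comparisons and the other none.

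**Working it through.** **Inputs.** From SAP Section 4.3: 100 completers per arm, two-sided 0.05, effect 0.28 SD. From Section 2: five primaries and three secondaries. From Section 5: ten headings. Two inputs are assumptions. The plan's 0.28 SD is a baseline-to-6-month change within an arm, and it is reused here as a between-arm difference. The documents give no correlation between outcomes; 0.5 is used, with a range of 0.3 to 0.7.

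**Step 1: reproduce the plan's figure.** The exact two-sided paired t-test with n = 100 and 0.28 SD has power 0.792 (normal approximation 0.800), against .800 in Table 4. At 0.33 SD it is 0.905, against .905. All 18 cells of Table 4 agree to within 2 points. The table uses burden alone at an unadjusted 0.05.

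**Step 2: first Holm threshold.**
- Five primaries: 0.05/5 = 0.010.
- Ten headings: 0.05/10 = 0.005.
- Four USE areas counted separately: 10 − 1 + 4 = 13, so 0.05/13 = 0.00385.

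**Step 3: between-arm power at the first step.** The noncentrality is 0.28 × √(100/2) = 1.98. In the normal approximation:
- At 0.010: 1 − Φ(2.576 − 1.98) = 0.276 (exact t 0.270).
- At 0.005: 1 − Φ(2.807 − 1.98) = 0.204 (exact t 0.199).
- With no adjustment at 0.05, exact t gives 0.504.

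**Step 4: full Holm procedure.** Simulation with 100,000 draws, noncentrality 1.98 on the five primaries, zero on the rest, correlation 0.5:

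| Family size | Average power per primary | Power for at least one primary |
|---|---|---|
| 5 | 0.33 | 0.60 |
| 8 | 0.25 | 0.53 |
| 10 | 0.22 | 0.49 |

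Over correlations of 0.3 to 0.7 the per-primary figures move by about 0.01. Power for at least one primary moves more: 0.68 down to 0.52 for five, and 0.57 down to 0.42 for ten. If the other five measures also have a 0.28 SD effect, the per-primary figure for ten is 0.25, against 0.33 to 0.34 for five.

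**Step 5: the within-arm reading.** USE has no baseline value and cannot enter a paired test, so at most nine headings remain. First-step paired power for burden at 0.28 SD is 0.489 at 0.05/9 = 0.0056, against 0.570 at 0.010. Section 5 also lists NPI-Q at baseline only. Taken literally, that removes its change score, and with it any change in the composite. Yet the protocol's Measures section exempts only bereaved caregivers from the six-month assessment of this outcome, which implies that others complete it.

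**The case against.** The strongest reply is that a flat family is legitimate and conservative. It controls error strongly over a wider set, and the Aim 2 hypothesis covers primary and secondary outcomes alike, so adjusting over both matches the stated claim. This stands as far as the secondaries go, and it is why they should stay under error control through a gate. It does not justify including USE, which the protocol calls a program evaluation measure, or a composite of existing members.

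Four stronger readings are tempting, and the documents do not support them.

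- **That the SAP puts everything in Section 5 into the family.** It speaks of multiple outcome measures, does not say all, and lists none. It assigns no test to the composite. The flat family of ten is the plain reading, not a stated fact.
- **That the family has 14 tests.** This requires splitting NPI-Q into separate severity and distress tests, which the SAP does not specify.
- **That primaries certainly lose alpha to USE in the between-arm comparison.** The sentence sits in the within-arm paragraph, where USE cannot enter. The loss arises only if the rule extends to between-arm tests.
- **That the trial could readily be declared a success on PAC or the composite alone.** The SAP defines no success rule. If the extra measures have no effect, a non-primary is rejected with no primary rejected in only about 1% of simulated trials. With real effects on the extras as well as the primaries, this rises to 5 to 22%, over families of 8 to 14 and correlations of 0.3 to 0.7.

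**Conclusion.** The point holds. The confirmatory family is not enumerated, its plain reading mixes primaries with measures that have no confirmatory role, and nothing in either document gives the primary/secondary split a part in testing. It is also unclear whether the adjustment reaches the between-arm tests, which are the ones that address the Aim 2 hypothesis.

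If it does, moving from ten headings to the five primaries doubles the first Holm threshold from 0.005 to 0.010. It also raises average power per primary from about 0.22 to 0.33, or from 0.25 to 0.33–0.34 if the extras share the effect. These sizes depend on treating 0.28 SD as a between-arm effect, on 100 completers per arm and on the assumed correlations. A reader might infer that narrowing the family rescues the trial's power. It does not: power stays far below 80%, because the plan's 80% belongs to a within-arm test of burden at an unadjusted 0.05. This is a cheap improvement in clarity and efficiency. The existing rule does control error over whatever family it is applied to.

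**What to change.** In SAP Section 6, before any unblinded analysis:

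1. State that the family-wise error rate is controlled at two-sided 0.05 by Holm, over one named between-arm test for each of the five primary outcomes, listed by name.
2. Test the three secondaries as a second, gatekept family only after the primary family is passed, and define what passing means. Requiring rejection of all five primaries is the simple version and costs the primaries nothing. If the gate stays closed, report the secondaries with nominal p-values and 95% confidence intervals as supportive.
3. Place the composite and the USE areas outside the family as exploratory.
4. Replace the reference to two outcomes with the named outcomes. Make the 0.05 rule refer to adjusted p-values for the confirmatory tests, and treat the within-arm paired tests as descriptive.
5. Label each Section 5 heading primary, secondary or exploratory.
6. Reconcile the baseline-only time frame for NPI-Q with its use as a change score.

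The cost is a few sentences and ten labels, with no added participants or data. The downside is that secondary results may be only supportive. With average power near 0.33 per primary, a gate requiring all five opens in at most about a third of trials under these assumptions. Findings on the composite and USE could be only exploratory.

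### SAP section 6 plans up to four between-arm tests per outcome and does not say which one decides or which p-value enters the multiplicity adjustment

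*SAP*

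**What the plan says.** SAP section 6 sets out these between-arm comparisons:

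- **Tests 1 and 2, at 6 months:** "We will compare the two arms at 6-month follow-up using the two-sample t-test and Wilcoxon rank sum test for each of the two outcomes". The two outcomes are not named. Section 2 lists more than two: "Primary outcome measures will include burden, depression, social support, and caregiver's health and interaction with health care providers".
- **Test 3, pre-post model:** "A pre-post analysis will be conducted to model the outcomes at 6-month follow-up to test the intervention arm and covariates adjusting the baseline measurements".
- **Test 4, longitudinal model:** "The two arms will also be compared incorporating observations from baseline and follow-up in longitudinal analysis of covariance (ANCOVA) models or linear mixed-effects models". Its contrast is specified: "the interaction effect between the treatment arm and follow-up time (while adjusting for covariates) will be tested in the longitudinal analysis".

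Three further rules bear on how these are read:

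- **Level:** "All tests will be two-sided and a p-value less than or equal to 0.05 will be reported as statistically significant".
- **Multiplicity:** adjustments, with Holm-Bonferroni and Hochberg given as examples, "will be implemented to control the family wise error rate when testing multiple outcome measures in Section 5".
- **Normality:** after an Anderson-Darling test, "If normal assumption is significantly violated then only nonparametric estimates and tests" are to be reported. The same sentence then allows transformation for later model-based testing.

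The Protocol's Data Analysis section has the t-test, the rank-sum test, the longitudinal ANCOVA and the same normality rule. It has no pre-post model and no multiplicity adjustment.

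**The concern.** The trial's hypothesis is between-arm: GP4C caregivers should improve more than R4C caregivers. For one outcome the plan can yield four p-values that bear on it, with no stated order of precedence. The multiplicity step needs one p-value per outcome and is not told which. It therefore cannot be run as written without a choice, and that choice could be made after the data are seen.

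Two things are at stake. If any of the tests may support a claim, the false-positive rate is higher than the plan implies. And the answer on burden, the outcome used for power, could turn on which test is put forward. Under randomisation the t-test, the pre-post model and the interaction target the same mean difference but with different precision. The rank-based and transformed analyses also change what is estimated.

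**Working it through.** **The plan's own figure.** SAP section 4.3, Table 4, gives power .800 for a two-sided paired t-test with n = 100 and 0.28 SD. The normal approximation gives Φ(0.28 × √100 − 1.96) = Φ(0.84) = 0.800; the noncentral t gives 0.792. All 18 cells of the table agree within one percentage point. But this is a within-arm test of change, so it does not indicate which between-arm test is meant to decide.

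**Inputs.** From the documents: two-sided 0.05, 1:1 allocation, 100 completers per arm. Assumed: baseline to 6-month correlation ρ = 0.3, 0.5, 0.7 (not given in the documents), normal data, no covariates, no missing data. On these terms, with the arms left free at baseline, the interaction test equals a t-test on change scores.

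**Type I error for one outcome, any test at p ≤ 0.05** (simulation, 120,000 trials per setting):

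| | ρ = 0.3 | ρ = 0.5 | ρ = 0.7 |
|---|---|---|---|
| Each test alone | about 5% | about 5% | about 5% |
| Any of four | 9.9% | 10.5% | 10.7% |
| Any of t-test, rank-sum, pre-post | 7.2% | 8.1% | 9.0% |

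The third row applies if the longitudinal model adjusts for baseline or constrains the baseline means to be equal, because it then nearly duplicates the pre-post model. Shorter runs of 20,000 to 40,000 trials gave 9.8% to 11.2% for any of four, and 7.5/8.2/9.3% for the third row. If the normality rule drops the t-test, the other three tests (interaction as change score) give 9.7% to 10.3% for ρ from 0.3 to 0.8. Four independent tests would give 1 − 0.95⁴ = 18.5%, which is too high here because the tests are correlated.

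**Family-wise error after Holm.** Take five independent primary outcomes, all null. Holm rejects something if the smallest p-value is at most 0.05/5 = 0.01.

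- One p-value per outcome: 1 − 0.99⁵ = 4.9%.
- Smallest of four per outcome: the chance of p ≤ 0.01 is 2.18/2.30/2.40%, so 1 − (1 − 0.0218)⁵ = 10.4%, and likewise 11.0% and 11.4%. A run of 20,000 trials gave 2.4/2.5/2.5%, slightly higher.

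**Precision.** Residual variance is proportional to 1 − ρ² for the pre-post model and 2(1 − ρ) for change scores, a ratio of (1 + ρ)/2 = 0.65/0.75/0.85. Assume a between-arm difference of 0.28 SD (Table 4 uses 0.28 only within arm). The noncentrality is then 0.28 × √(100/2) = 1.98, divided by √(1 − ρ²) or √(2(1 − ρ)).

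- Pre-post model: Φ(1.98/√0.91 − 1.96) = 55%, then 63% and 79%.
- Interaction as change score: Φ(1.98/√1.4 − 1.96) = 39%, then 51% and 72%.
- 6-month t-test about 50%; rank-sum about 49%.

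Under that assumption the four tests are not unanimous in 36/39/45% of simulated trials.

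**Skewed case.** For an assumed 0-30 score with skewness 1.5 and a 0.28 SD shift, power is 68/70/69% for the rank-sum test and 56/63/78% for the pre-post model.

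**The case against.** **The interaction test is already the primary one.** This is the strongest defence: section 6 says that test is there to evaluate the difference between the arms. But the longitudinal comparison is introduced as an additional one, its model is a choice of two, and the pre-post model is equally mandatory. The text gives it no priority.

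**The multiplicity adjustment protects each outcome.** In part it does. A reader might infer that every test is finally read at 0.05, so that each outcome's final error exceeds 5%. The SAP does not support that, because it commits to adjusting across the section 5 outcomes and 0.05 is the level before that step. At a threshold of 0.01, any-of-four gives only about 2.2% to 2.5% for one outcome. What the adjustment does not hold at 5% is the family-wise rate, if the smallest of several p-values is fed in.

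**The normality rule selects the test.** It settles only t-test against rank-sum. A reader might also infer that it displaces the model results when normality fails. That reading is weak: its list names simple summaries and Wilcoxon tests, and the sentence goes on to further model-based testing. What stays open is whether the model is reported on the raw or the transformed scale.

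**The size depends on an unstated model.** This stands. The 10-11% takes the interaction as a change-score test; otherwise the figure is about 7-9%.

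**Naming any one analysis would cure the gap.** This also stands. The preference for the pre-post model rests on precision, and the skewed case shows that it is not always the most powerful choice.

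**Conclusion.** The point holds as an omission that should be corrected. Up to four between-arm tests are planned for an outcome, none is designated to decide, and the p-value for the multiplicity step is not identified. If significance on any of them counts, the error rate roughly doubles at the level in force: about 10-11% instead of 5% for one outcome before adjustment, and about 10-11% family-wise for five independent outcomes under Holm. For one outcome it is about 7-9% if the longitudinal model is baseline-adjusted.

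These figures rest on 100 completers per arm, normal data, assumed correlations of 0.3 to 0.7, complete data and no covariates. Outcomes not among the unnamed two would have fewer tests and less inflation. The documents do not say that the most favourable test will be chosen; they only leave that possible.

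**What to change.** - Name the SAP's pre-post model (6-month score on arm and baseline score, covariates listed in advance, raw scale) as the single primary between-arm analysis for burden and the other scale scores measured at both times. Report it whatever the Anderson-Darling result.
- Label the t-test, rank-sum, transformed and longitudinal analyses as sensitivity analyses.
- Pass only that one p-value per outcome to one stated procedure, for example Holm, over a stated family.
- Before fixing the family, reconcile the NPI-Q entry in SAP section 5: its title describes change from baseline at 6 months, but its time frame says baseline only. This also decides whether the composite distress score, which uses NPI-Q distress, can belong. A reader might infer that NPI-Q should simply be left out. The documents do not support that, since section 6 has primary and secondary outcomes assessed at both times.
- Bring the Protocol's Data Analysis section into line.

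Scoring of the NSOC items, the test for the single self-rated health item and the handling of USE are separate details.

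**Cost.** No new data: the model is already in the SAP and baseline values are collected. The team must settle the covariate list and the family. The first Holm threshold is 0.05/5 = 0.010 for the five primary outcomes, 0.05/7 = 0.007 for the seven with both time points stated, and 0.05/9 = 0.0056 if NPI-Q and the composite join. The downside is less emphasis on rank-based results, which can be more powerful for strongly skewed outcomes with low baseline correlation.
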